**Table 1 Treatment Arm Schedule of Events**

Study Procedure	Screening/ Baseline	Surgical Visit Day 0	Day 1	Day 7	Day 28	Day 45
Visit	VISIT 1	VISIT 2	VISIT 3	VISIT 4	VISIT 5	VISIT 6
Windows for Visits	(Day -30 to 0)		+/- 3 days	+/- 3 days	+/- 3 days	+/- 3 days
Inclusion/Exclusion	X					
Informed Consent	X					
Demographics	X					
Medical History and Concurrent Illnesses	X					
Concomitant Medications	X					
Pregnancy testing as indicated/appropriate		X				
Subject reported AEs prior to or after surgery	X	X	X	X	X	X
Randomization with subsequent intracanalicular dexamethasone insert placement		X				
Easy of insertion		X				
If dilator was used		X				
Document administration of prescribed medications			X	X	X	X
Ocular Pain Assessment (FLACC)	X		X	X	X	X
Distance VA testing	X		X	X	X	X
BCVA (ETDRS at 4m)	X		X	X	X	X
Anterior chamber cell count	X		X	X	X	X

Study Procedure	Screening/ Baseline	Surgical Visit Day 0	Day 1	Day 7	Day 28	Day 45
Visit	VISIT 1	VISIT 2	VISIT 3	VISIT 4	VISIT 5	VISIT 6
Windows for Visits	(Day -30 to 0)		+/- 3 days	+/- 3 days	+/- 3 days	+/- 3 days
Anterior chamber cell flare	X		X	X	X	X
Punctum examination	X	X	X	X	X	X
Insert Visualization and ease of visualization score			X	X	X	X
Intraocular Pressure	X		X	X	X	X
Ophthalmic Examination (dilated fundus exam)	X		X	X	X	X
Satisfaction Survey						X

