**Table 2 Control Arm Schedule of Events**

Study Procedure	Screening/ Baseline	Surgical Visit Day 0	Day 1	Day 7	Day 28	Day 45
-----------------	------------------------	-------------------------	-------	-------	--------	--------

Visit	VISIT 1	VISIT 2	VISIT 3	VISIT 4	VISIT 5	VISIT 6
Windows for Visits	(Day -30 to 0)		+/- 3 days	+/- 3 days	+/- 3 days	+/- 3 days
Inclusion/Exclusion	X					
Informed Consent	X					
Demographics	X					
Medical History and Concurrent Illnesses	X					
Concomitant Medications	X					
Pregnancy testing as indicated/appropriate		X				
Subject reported AEs prior to or after surgery	X	X	X	X	X	X
Randomization without intracanalicular dexamethasone insert placement		X				
Document administration of prescribed medications			X	X	X	X
Ocular Pain Assessment (FLACC)	X		X	X	X	X
Distance VA testing	X		X	X	X	X
BCVA (ETDRS at 4m)	X		X	X	X	X
Anterior chamber cell count	X		X	X	X	X
Anterior chamber cell flare	X		X	X	X	X
Punctum examination	X	X				
Intraocular Pressure	X		X	X	X	X

Study Procedure	Screening/ Baseline	Surgical Visit Day 0	Day 1	Day 7	Day 28	Day 45
Visit	VISIT 1	VISIT 2	VISIT 3	VISIT 4	VISIT 5	VISIT 6
Windows for Visits	(Day -30 to 0)		+/- 3 days	+/- 3 days	+/- 3 days	+/- 3 days
Ophthalmic Examination (dilated fundus exam)	X		X	X	X	X
Satisfaction Survey						X

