#### **Visit 2 Surgical Visit ( Day 0)**

- Subject reported AE's prior to surgery
- Indicate the incision type, location, and size (mm)
- Punctum examination
- If you are a patient who could possibly be pregnant (you have started menstruation), a urine pregnancy test will be performed, and it must be negative in order to continue in the study.
- Randomization and potential placement of intracanalicular dexamethasone insert if assigned to treatment arm
- Record any surgical complications

**Visit 3 (Day 1 +/- 3 days) Visit 4 (Day 7 +/- 3 days) Visit 5 (Day 28 +/- 3 days)  
Visit 6 (Day 45 +/- 3 days)**

- Subject reported AE's after surgery
- Document administration of prescribed medication (if used and number of drops used)
- Ocular Pain Assessment (FLACC)
- Distance VA testing, when applicable
- Best-corrected visual acuity as measured by ETDRS or HOTV chart at 4m based on patient age (HOTV for pre-literate patients)
- Anterior chamber cell count
- Anterior chamber cell flare
- Punctum examination and ease of insert visualization (for patients receiving DEXTENZA insert only)
- Intraocular pressure
- Ophthalmic Examination including dilated fundus exam
- Satisfaction Survey (at the end of visit 6 only)

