## 6. SAFETY DEFINITIONS, REPORTING, AND MONITORING

Safety will be assessed from surgery through 45 days post surgery. Safety will be assessed only by frequency and incidence of events of special interest (ESI) and SAEs.

Monitoring for ESIs and SAEs will occur from the initial study-specific procedure through 28 days post last study drug dose (including the weaning doses).

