### 6.1.3 Events of Special Interest

The patients enrolled in this trial will have trauma to the eye as a direct result of surgery with known and previously reported potential significant eye-related events. The following events will not be included in the primary safety outcome, but they are clinical events of special interest (ESI) that may relate to safety and that will be tracked and reported in the trial results. These AEs are to be reported to study database, regardless of whether these events meet serious criteria or unexpectedness:

- Elevated intraocular pressure
- Eye pain and local erythema
- Infection
- Allergic reaction
- Trauma to the punctum
- Eyelid swelling
- Hazy or cloudy vision
- Feeling like something is in the eye
- Increased sensitivity to light

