## **8. STATISTICAL CONSIDERATIONS**

### **8.1 Sample Size Considerations and Analysis Plan**

This is a feasibility study and the sample size of 30 is not designed to provide power to determine any differences between arms.

Analysis results will be presented by study drug vs. standard of care topical drops overall and by surgical procedure group.

Descriptive statistics such as number of observations, mean, median, standard deviation, minimum and maximum will be presented by treatment arms for continuous variables (such as age, weight, etc.). Other descriptive statistics such as counts, proportions, and/or percentages will be presented by group to summarize discrete variables (such as race, sex, etc.).

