#### **8.1.2 Safety**

The safety reports will be summarized.

Serious adverse events will be presented overall. Severity and relationship to study drug will be provided.

Events of special interest will be presented overall and summarized by participant characteristics.

Prior and concomitant medications will be summarized by World Health Organization (WHO) drug class.

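### After Day 0 the punctum is examined only in the insert arm, so mild local signs are somewhat more likely to be recorded there than in controls

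*Combined protocol and SAP*

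**What the plan says.** **Schedule.** The Table 1 row for the insert arm reads "Punctum examination X X X X X X", which covers screening, Day 0 and all four follow-up visits. The matching row in Table 2 for controls reads "Punctum examination X X", which covers screening and Day 0 only. The list for Visits 3 to 6 in Section 5.2.1 has "Punctum examination and ease of insert visualization (for patients receiving DEXTENZA insert only". Taken alone, the parenthesis could be thought to qualify only the visualization, but Table 2 settles that it covers the punctum examination too. Table 1 already has a separate row for seeing the insert.

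**Safety outcomes.** Section 6 states: "Safety will be assessed only by frequency and incidence of events of special interest (ESI) and SAEs". The ESI list in Section 6.1.3 includes "Trauma to the punctum", infection, eyelid swelling, and a combined item for eye pain with local erythema. It adds: "These AEs are to be reported to study database, regardless of whether these events meet serious criteria or unexpectedness".

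**Presentation.** Section 8.1 states: "Analysis results will be presented by study drug vs. standard of care topical drops overall and by surgical procedure group". Section 8.1.2, on safety, says: "Events of special interest will be presented overall and summarized by participant characteristics". It does not mention arm.

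**Masking.** Section 3.1 describes an open-label study. Masked assessment is stated only for the FLACC score (Section 10.3).

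**The concern.** A between-arm comparison of adverse events is fair only if both arms are looked at equally hard. Here one arm has an additional scheduled look at the punctum at every follow-up visit, and the other has none.

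Three features make this worth attention. ESIs carry nearly all the non-serious safety evidence. They count whatever their severity, so mild signs enter the tables, and mild signs are the ones most dependent on somebody looking. Participants may be as young as 3, so self-report is a weak substitute for inspection.

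The interpretation of the local-safety table is at stake. Part of any excess of infection, redness or lid swelling in the insert arm could reflect the additional examination and not the product.

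**Working it through.** **1. Reproduce the sample size.** Section 4.1 gives two procedure groups, each with 10 insert and 5 control patients: 2 × (10 + 5) = 30, as stated. That is 2 × 10 = 20 insert and 2 × 5 = 10 control patients.

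**2. Count scheduled post-operative punctum examinations (Tables 1 and 2).**

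| | Insert | Control |
|---|---|---|
| Per patient, Visits 3 to 6 | 4 | 0 |
| Total | 20 × 4 = 80 | 10 × 0 = 0 |
| If scheduled for both arms | 20 × 4 = 80 | 10 × 4 = 40 |

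The per-patient row is the fair comparison, because the totals also reflect the 2:1 allocation.

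**3. List what the arms share at Visits 3 to 6.** Both tables mark adverse-event reporting, anterior chamber cell and flare, intraocular pressure, and an eye examination with dilated fundus view. Section 10.4 has cells and flare graded with a slit beam. Section 5.2.3 has the investigator record all adverse events. Detection in controls is therefore reduced, not absent. No external or lid examination is named in either arm.

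**4. Separate the events.**
- *Punctal trauma from insertion:* controls have no insertion and no scheduled dilator use, so a low control rate is expected whatever the schedule.
- *Infection, local erythema, eyelid swelling:* these can occur in either arm after surgery, laser or drops. Signs at the punctum or adjacent lid are where the additional look could matter.

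**5. Illustrate the size.** The documents give neither event rates nor detection rates, so these are assumptions: the same true risk *p* in both arms, full detection with the insert, and relative detection *s* in controls.

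Expected records are 20*p* (insert) and 10*ps* (control). The spurious risk difference is *p* − *ps* = *p*(1 − *s*).

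| *p* | *s* | Insert records | Control records | Spurious difference |
|---|---|---|---|---|
| 5% | 0.5 | 1.0 | 0.25 | 2.5 points |
| 10% | 1 | 2.0 | 1.0 | 0 |
| 10% | 0.75 | 2.0 | 0.75 | 2.5 points |
| 10% | 0.5 | 2.0 | 0.5 | 5 points |
| 20% | 0.5 | 4.0 | 1.0 | 10 points |

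**6. Check what a zero in controls would mean.** The probability of no recorded event in 10 controls is (1 − *ps*)^10. At *p* = 10% it is 0.90^10 = 0.349 with full detection and 0.95^10 = 0.599 with half. A zero is common in either case, so it does not by itself show that nobody looked. Unequal looking makes it more likely.

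**The case against.** The strongest reply is that this is ordinary device follow-up. The site of an insert is inspected in those who carry it, and Section 4.3 provides for removal if a related adverse event is found. Controls have no device, so insertion trauma is not expected in them. Only one of the nine ESI items names the punctum, and the protocol does not define how far the punctum examination reaches. Controls are still questioned and examined at the front of the eye at every visit. The study is an unpowered, descriptive feasibility study, Section 6.1.3 places ESIs outside the primary safety outcome, and Section 8.1.2 does not ask for them by arm. Any bias runs against the insert, so it would not hide harm from it.

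Most of this stands, and it limits the point. It does not remove it. Section 8.1 sets presentation by arm for the results generally, and a randomized control group invites that comparison. In a study without planned tests, the descriptive safety table is a main product, and unequal ascertainment distorts description too. The shared eye examination is specified only as covering the dilated fundus, so it cannot be assumed to match a dedicated look at the punctum.

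A reader might infer that local events would simply be missed in controls, or that a zero control rate would result wholly from not looking. The shared assessments contradict the former. The absence of insertion contradicts the latter for punctal trauma.

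**Conclusion.** The asymmetry is real and deliberate: four scheduled post-operative punctum examinations per insert patient and none per control. It makes mild punctal or adjacent lid signs more likely to be recorded with the insert and so partly biases the local-safety contrast against it. For insertion-related trauma it matters little.

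The size is unknown. The 2.5 to 10 points shown for *p* from 5% to 20% depend on an assumed *s* of 0.5 and on equal true risk; with *s* = 1 the bias is zero. The conclusion also assumes that a look at the punctum can reveal signs on the neighbouring lid, which the protocol does not spell out.

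Two stronger readings should be avoided. One is that the data would place no limit at all on the control rate of local events; that ignores the shared examinations and adverse-event reports. The other treats the 95% upper bound for 0 events in 10 (1 − 0.05^(1/10) = 26% one-sided; 1 − 0.025^(1/10) = 31% two-sided) as a measure of this bias. Those figures reflect only the number of controls and would apply to any event not seen in them.

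This is a modest weakness in interpretation, worth correcting because the correction is so cheap.

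**What to change.** In Table 2, mark the punctum examination at Days 1, 7, 28 and 45. In the Visit 3 to 6 list of Section 5.2.1, split the item: punctum examination for both arms, within the eye examination already done, and insert visualization for insert patients only. The cost is two text edits and a brief additional look at four existing visits in 10 controls (40 looks, no new visits). It equalizes the schedule but does not mask the examiner, so the open-label caveat remains.

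If this is not adopted, keep reporting every ESI in both arms, as Section 6.1.3 requires. Record which examination detected each event, flag those found only at the insert-arm punctum examination, and state in Section 8.1.2 that these are descriptive data for the insert arm and not a between-arm comparison. Do not restrict infection, erythema or swelling to what the shared examination finds, because that could drop insert-arm events that must be reported. The cost is one data field and a sentence.

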### **5.2.2 Unscheduled Visits**

All attempts should be made to keep patients on the study schedule. Unscheduled visits may be necessary to repeat testing following abnormal laboratory results, for follow-up of AEs, or for any other reason, as warranted.

### **5.2.3 Adverse Event Information Collection**

The investigator (or designee) will record all AEs that occur during the study

The definition of an AE and SAE, and information on the determination of severity and relationship to treatment are provided in Section 6.

## **5.3 Rescue Treatment**

Rescue treatment will be left to the discretion of the surgeon. Rescue treatment includes but is not limited to topical NSAID, oral and topical steroids. Rescue treatment will be adequately documented to include the dosage needed.

## 6. SAFETY DEFINITIONS, REPORTING, AND MONITORING

Safety will be assessed from surgery through 45 days post surgery. Safety will be assessed only by frequency and incidence of events of special interest (ESI) and SAEs.

Monitoring for ESIs and SAEs will occur from the initial study-specific procedure through 28 days post last study drug dose (including the weaning doses).

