### 2.2 Secondary Objectives

- Incidence and severity of adverse events from baseline through post-op day 45
- Degree of inflammation (AC cell count)
- Resolution of inflammation as defined as either 0 or 0.5 or less cell on follow up post op exams
- Resolution of pain using the FLACC Behavioral Pain Rating Scale
- Ratio of Intraocular pressure increase with insert
- % of patients with rebound inflammation from baseline through post-op care
- % of patients that were given supplementary prednisolone drops and the number of drops needed in these patients

- Mean change in BCVA from baseline over time using either ETDRS or HOTV chart testing depending on age
- Primary caregiver's ability to adhere to treatment plan as prescribed and therapeutic preferences measured with primary caregiver satisfaction survey

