## 6.2 Recording and Reporting Adverse Events

All ESIs and SAEs will be recorded in the study database.

All SAEs, regardless of assessment of causal relationship to study insert will be reported to the sponsor. The sponsor will provide these reports to Ocular Therapeutix.

The investigator will promptly report to the IRB all unanticipated problems involving risks to patients. This includes death from any cause and all SAEs

related to the use of the study insert. All SAEs will be reported to the IRB, regardless of assessed causality.

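### Severity of adverse events is a secondary endpoint, but the plan has no severity scale and, followed as written, neither grades nor reports severity for non-serious events

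*Combined protocol and SAP*

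**What the plan says.** The Synopsis and Section 2.2 list the same first secondary item: "Incidence and severity of adverse events from baseline through post-op day 45".

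Section 5.2.3 sets wide collection, "The investigator (or designee) will record all AEs that occur during the study", and says that "information on the determination of severity and relationship to treatment are provided in Section 6".

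Section 6 opens with a narrower rule: "Safety will be assessed only by frequency and incidence of events of special interest (ESI) and SAEs". Section 6.1 defines an adverse event (AE) and an SAE and lists nine types of ESI. Section 6.2 names what enters the database: "All ESIs and SAEs will be recorded in the study database".

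Section 8.1.2 has one paragraph on SAEs, "Serious adverse events will be presented overall. Severity and relationship to study drug will be provided", and a separate one on ESIs, "Events of special interest will be presented overall and summarized by participant characteristics".

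**The concern.** An endpoint with two parts needs a rule for recording and a rule for reporting each part. Incidence has both. For non-serious events, severity has neither: Section 6 excludes it, the ESI paragraph of Section 8.1.2 does not mention it, and no scale is defined.

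Section 6.1.3 requires ESIs to be captured whether or not they meet the criteria for seriousness, so the protocol itself expects non-serious events. Under the plan, a faint and a pronounced eyelid swelling would each count as one ESI with nothing to tell them apart. The trial is descriptive, so a full description of tolerability is a large part of what it can deliver. A grade not recorded when the event occurs may not be recoverable later.

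**Working it through.** **1. The text, side by side.** The plan states no safety figure to reproduce, so the first step is a comparison of sections.

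| Place | Events covered | Severity |
|---|---|---|
| Synopsis; Section 2.2 | Adverse events | Named in the endpoint |
| Section 5.2.3 | All AEs | Said to be explained in Section 6 |
| Section 6, opening | ESIs and SAEs | Excluded by the word *only* |
| Sections 6.1.1 to 6.1.3 | Definitions of AE, SAE, ESI | No grade or scale |
| Section 6.2 | ESIs and SAEs to the database | Not mentioned |
| Section 8.1.2, SAE paragraph | SAEs | To be provided |
| Section 8.1.2, ESI paragraph | ESIs | Not mentioned |

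The criteria in Section 6.1.2 define seriousness, which is not severity. So even the SAE severity that Section 8.1.2 promises has no stated scale. AEs that are neither ESIs nor SAEs are to be recorded under Section 5.2.3, but have no stated database entry or summary.

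**2. Which ESIs lose most.** Tables 1 and 2 schedule IOP, the FLACC pain score, acuity (BCVA), and anterior chamber cell and flare at baseline and at every postoperative visit in both arms. Against the nine ESI types in Section 6.1.3:

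- Three have a scheduled numerical counterpart: elevated IOP (the reading), eye pain (FLACC, 0 to 10) and hazy vision (BCVA, in part).
- The other 9 − 3 = 6 have no scheduled graded measure: infection, allergic reaction, punctal trauma, eyelid swelling, foreign-body sensation and light sensitivity. The punctum is examined, but no grade is given for the finding.

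**3. How much an SAE-only severity summary could hold.** Inputs: n = 30 in total, from two procedure groups of 10 insert and 5 control each, so 2 × 10 = 20 insert and 2 × 5 = 10 control (Section 4.1). The documents give no SAE rate, so the risk p per child is an assumption, shown as a range.

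- Expected children with an SAE = 30p
- P(no SAE among n children) = (1 − p)^n
- P(at most two of 30) = sum over k = 0, 1, 2 of C(30, k) p^k (1 − p)^(30 − k)

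| Assumed p | Expected in 30 | No SAE in 30 | At most 2 in 30 | No SAE in 20 insert | No SAE in 10 control |
|---|---|---|---|---|---|
| 1% | 0.3 | 0.99^30 = 74% | 99.7% | 82% | 90% |
| 3% | 0.9 | 0.97^30 = 40% | 94% | 54% | 74% |
| 5% | 1.5 | 0.95^30 = 21% | 81% | 36% | 60% |
| 10% | 3.0 | 0.90^30 = 4% | 41% | 12% | 35% |

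**4. What grading ESIs would add.** No ESI rate is given either. If 20% to 50% of children had at least one ESI (an assumption), 30 × 0.2 = 6 to 30 × 0.5 = 15 children would have a graded event: 4 to 10 with the insert and 2 to 5 controls.

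**The case against.** **The severity sentence in Section 8.1.2 may be meant for all events.** It names no event type, and Section 5.2.3 promises a severity rule alongside the recording of all AEs. The wider reading is possible. Against it, the sentence follows directly on the SAE sentence, the ESI paragraph is silent on severity, and Section 6 says *only*. Even on the wider reading, the scale is missing and Section 6 contradicts Section 8.1.2.

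**A reader might infer that the severity part will rest on few or no events.** The documents do not support *will*. They give no SAE rate, and Section 6.1.2 defines SAEs broadly, including important medical events. At an assumed 10%, about three children with an SAE are expected and an empty summary is unlikely.

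**A reader might infer that a marked rise in pressure or severe pain would vanish into a count.** It would not. IOP and FLACC are measured at visits, IOP increase is a separate secondary endpoint, and pain is the primary endpoint. This part of the objection stands and narrows the loss to events without such a measure, and to events between visits.

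**This is a feasibility study.** Section 8.1 says so: "This is a feasibility study and the sample size of 30 is not designed to provide power to determine any differences between arms". Severity would therefore be described, not tested, and no between-arm conclusion is lost. But lack of power does not explain leaving half of a named endpoint without a scale or a summary.

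**Conclusion.** The point holds as a conflict in the text with a practical consequence. The endpoint names severity, Section 6 excludes it, Section 8.1.2 attaches it to SAEs and not to ESIs, and the reference from Section 5.2.3 leads to a rule that does not exist. Followed as written, severity of non-serious events is neither graded nor reported. The loss falls mainly on the six ESI types without a scheduled graded measure.

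That SAE-only severity is *likely* to rest on few events is an inference from the sample size and assumed risks. Up to an assumed 5% risk, the chance of at most two children with an SAE is 81% or more; at 10% it is 41%. It should not be put more strongly, and it should not be read as a claim that pressure or pain data are lost or that a comparison of arms fails.

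This should be corrected. It does not affect the primary endpoint.

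**What to change.** 1. **Section 6, opening.** Replace the restriction to frequency and incidence with assessment *by incidence and worst severity*. This wording occurs in Section 6 and not in Section 8.1.2, so it is changed in one place.
2. **Section 6, new paragraph.** Define mild, moderate and severe, for example by how far the event interferes with the child's usual activities. The reference in Section 5.2.3 then leads somewhere.
3. **Recording (Sections 5.2.3 and 6.2).** Enter a grade for every ESI, SAE and other recorded AE when the event is entered, and state that all of these go into the database. Where a concurrent IOP reading or masked FLACC score exists, report it beside the grade. These measures are scheduled only at visits, so they supplement the grade and do not replace it.
4. **Section 8.1.2.** State that severity is given for ESIs and other AEs as well as SAEs, as each child's worst grade by arm, with a listing by procedure group. For the ESIs, a table split by procedure group as well would have 9 types × 3 grades × 2 arms × 2 groups = 108 cells for 30 children; a listing is easier to read.

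Cost: one form field, a little recording time, one descriptive table and a paragraph of protocol text. Events without a measurement would be graded by staff who know the assignment, and the report should say so.

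If the sponsor does not want to grade non-serious events, the alternative is to narrow the secondary endpoint to what will be reported. That removes the contradiction but gives up the information, and SAE severity would still need a scale.

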### Secondary Endpoints:

- Incidence and severity of adverse events from baseline through post-op day 45
- Degree of inflammation (AC cell count)
- Resolution of inflammation as defined as either 0

---

or 0.5 or less cell on follow up post op exams

- Resolution of pain using the Face, Legs, Activity, Cry, Consolability (FLACC) Behavioral Pain rating Scale. Ratio of Intraocular pressure increase with insert
- % of patients with rebound inflammation from baseline through post-op care
- % of patients that were given supplementary prednisolone drops and the number of drops needed in these patients
- Mean change in BCVA from baseline over time using either ETDRS or HOTV chart testing depending on age
- Primary caregiver's ability to adhere to treatment plan as prescribed and therapeutic preferences measured with primary caregiver satisfaction survey

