### **4. SELECTION, WITHDRAWAL, AND REPLACEMENT OF PATIENTS**

#### **4.1 Study Population**

The study aims to enroll 30 pediatric patients undergoing routine retinal surgery or laser treatment under anesthesia. Patients in each treatment group (surgery or laser) will be randomized 2:1 at the time of surgery/laser to receive either:

- 3) Treatment Arm: Dextenza insert intraoperatively for perioperative ocular inflammation and pain. These patients will not be prescribed topical steroid drops post-operatively, or
- 4) Control Arm: Prednisolone forte 1% steroid drop taper for 28 days post-operatively to treat perioperative ocular inflammation and pain; drops four times per day (QID) on days 0-7, three times per day (TID) on days 7-14, twice per day (BID) on days 14-21 and once per day (QD) on days 21-28.

Each treatment group (surgery or laser) will include 15 patients total, 10 receiving Dextenza and 5 receiving the control drug. Drops for dilation and antibiotic coverage will be used as clinically indicated in all groups throughout the study period. Follow up will occur at post-op day 1, 7, 28/30 and 45 (+/- three days for all post-operative timepoints).

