## **4.2 Treatment Logistics and Accountability**

### **4.2.1 Packaging, Labeling, and Storage**

Intracanalicular dexamethasone insert must be stored in a secure area accessible only to the Investigator and their designee(s) and refrigerated and stored between 2° C and 8° C. Intracanalicular dexamethasone insert contains 0.4 mg dexamethasone and is designed to provide a sustained and tapered release of therapeutic levels of dexamethasone to the ocular surface for up to 30 days for the reduction of post-surgical inflammation and pain associated with ocular surgery. Dexamethasone is an anti-inflammatory 9-fluoro-glucocorticoid (also termed a glucocorticoid agonist) and is the active ingredient found in

MAXIDEX® 0.1% (dexamethasone ophthalmic suspension), which contains approximately 50 µg of dexamethasone per drop.

Study inserts will be supplied by Ocular Therapeutix in a sealed foil pouch containing one intracanalicular dexamethasone insert in a foam carrier.

Study inserts will be shipped to the site via overnight shipping using cold packs to maintain a temperature of 2° to 8° C. The Investigator, or an approved representative (e.g. pharmacist), will ensure that all study drug inserts are stored in a secured area, under recommended storage conditions and in accordance with applicable regulatory requirements. The shipping box is to be opened and stored immediately at the site in a refrigerator intended for investigational products at a temperature of 2° to 8°C.

When the insert is removed from the refrigerator, it should be visually inspected. Exposure of the insert to temperatures outside these limits is not recommended. Records of actual storage conditions (i.e. temperature log) at the study site must be maintained; and must include a record of the dates, when the refrigerator was checked, the initials of person checking, and the temperature.

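### Section 6 sets two incompatible windows for the same safety events, and the dose-anchored one ends at Day 45 on no reading of the last dose

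*Combined protocol and SAP*

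**What the plan says.** Section 6 first gives a calendar window: "Safety will be assessed from surgery through 45 days post surgery". It then limits what counts: "Safety will be assessed only by frequency and incidence of events of special interest (ESI) and SAEs". The next paragraph gives those same two event types another window: "Monitoring for ESIs and SAEs will occur from the initial study-specific procedure through 28 days post last study drug dose (including the weaning doses"). The synopsis and Section 2.2 add a third, for the adverse event endpoint: "Incidence and severity of adverse events from baseline through post-op day 45".

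The dosing days come from Section 4.1. The treatment arm receives "Dextenza insert intraoperatively for perioperative ocular inflammation and pain", and "These patients will not be prescribed topical steroid drops post-operatively". The control arm's prednisolone taper has its last step on Days 21 to 28. Section 4.2.1 says the insert delivers dexamethasone "to the ocular surface for up to 30 days". The last scheduled visit in both arms is Day 45, plus or minus 3 days. Nothing in the protocol says what a last dose means for a sustained-release insert.

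**The concern.** A window counted from the last dose depends on the product. One arm is dosed once, in theatre, and the other for four weeks, so the same 28-day rule can close on different calendar days in the two arms. Section 8.1 presents results for the insert against the drops, Section 6 uses frequency and incidence, and no adjustment for time at risk is planned. If the windows differ, the arm with the longer window has more chance to record an event.

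The later weeks matter for this product. Elevated intraocular pressure is a listed ESI (Section 6.1.3), and pressure is measured at the Day 28 and Day 45 visits. Under one reading, the insert's window closes before its stated release period has ended. The study is also open-label, so a judgement about whether a late event is inside the window may be made by someone who knows the arm.

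**Working it through.** **Inputs**

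- Stated end of the safety window: Day 45, both arms (Section 6, first paragraph).
- Rule: last study drug dose + 28 days (Section 6, second paragraph).
- Insert placement: Day 0 (Section 4.1). Insert release: up to Day 30 (Section 4.2.1).
- Last taper drop: Day 28 (Section 4.1).
- Visit 5: Day 28 ± 3, so Days 25 to 31. Visit 6: Day 45 ± 3, so Days 42 to 48 (Tables 1 and 2).

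**Step 1: try to reproduce Day 45.** End = last dose + 28, so an end on Day 45 needs a last dose on Day 45 − 28 = 17. Neither arm has its last dose then. The insert was placed on Day 0, and the control taper is still in its Day 14 to 21 step.

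**Step 2: apply the rule under each reading.**

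| Reading of the last dose | Last dose | Window ends | Against Day 45 | Against Visit 6 (Days 42–48) |
|---|---|---|---|---|
| Insert: placement | Day 0 | 0 + 28 = Day 28 | 17 days before | 14 to 20 days before |
| Insert: end of release | up to Day 30 | by 30 + 28 = Day 58 | up to 13 days after | up to 10 to 16 days after |
| Drops: last taper drop | Day 28 | 28 + 28 = Day 56 | 11 days after | 8 to 14 days after |
| Drops: not study drug | none | undefined | – | – |

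**Step 3: gap between arms.** With placement and last drop, 56 − 28 = 28 days. With end of release and last drop, 56 − 58 = −2 days, so the gap almost vanishes.

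**Step 4: the start.** The three statements begin at surgery, at baseline and at the first study-specific procedure. Screening may fall anywhere from Day −30 to Day 0, so the starts can differ by up to 30 days. This affects both arms alike, but it changes which pre-surgery events are counted.

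**Step 5: what the literal reading would exclude.** All of Visit 6 lies outside an insert window that closes on Day 28. So does a Visit 5 held on Days 29 to 31, which its own visit window allows.

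**Step 6: illustration of size.** The documents give no event rates, so the 28-day risk p is an assumption, varied from 10% to 30%. Assume a constant hazard, equal in both arms. Follow controls to Day 45, since no later contact is scheduled, and count insert events only to Day 28. Apparent control risk = 1 − (1 − p)^(45/28), with 45/28 = 1.607.

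| p (insert, to Day 28) | Control, to Day 45 | Spurious difference |
|---|---|---|
| 10% | 1 − 0.9^1.607 = 15.6% | 5.6 points |
| 20% | 1 − 0.8^1.607 = 30.1% | 10.1 points |
| 30% | 1 − 0.7^1.607 = 43.6% | 13.6 points |

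**The case against.** The strongest reply is that the data will exist. Tables 1 and 2 collect subject-reported adverse events and intraocular pressure at every follow-up visit through Day 45 in both arms. Section 5.2.3 requires all adverse events during the study to be recorded, and intraocular pressure increase is also a secondary endpoint in its own right. To lose insert-arm events after Day 28, someone would have to set aside scheduled data against the first sentence of Section 6. This stands, and it limits the point to a risk of the wording.

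A reader might infer that the insert will be watched for half as long as the drops, 28 days against 56, and will therefore look safer. The documents do not establish this. Day 28 requires the last dose to mean placement, which is undefined; end of release removes nearly all of the gap. Day 56 requires the drops to be study drug. The reference to weaning doses supports that, but the synopsis names only the insert as study drug and Section 8.1 contrasts study drug with the drops. Rescue steroids (Section 5.3), if counted, would move the end patient by patient.

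A reader might also double the exposure and obtain 19%, 36% and 51% from 1 − (1 − p)², a difference of 9 to 21 points. That credits controls with full ascertainment to Day 56, when no visit falls after Day 48. Even the smaller figures in the illustration rest on a constant hazard. Section 6.1.3 links the ESIs to surgical trauma, and if events cluster early the extra days add less.

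Finally, Section 8.1.2 presents SAEs and ESIs overall, and the study is a 30-patient feasibility study with no safety test or decision rule. That lowers the stakes. It does not remove the by-arm presentation in Section 8.1, where overall is set against procedure group and not against arm.

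**Conclusion.** The contradiction is certain: Section 6 gives two end points for the same events, and no reading of the dosing days reconciles them. The size of any effect on the comparison between arms is not certain. It runs from almost nothing (end-of-release reading, or the Day 45 sentence followed in both arms) to roughly 6 to 14 percentage points in favour of the insert. The upper range assumes the placement reading, insert data after Day 28 left out, controls counted to Day 45, an equal constant hazard and 28-day risks of 10% to 30%. The documents do not support saying that the insert arm will in fact be under-observed.

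The text should still be corrected. One stated rule, taken literally, gives windows that depend on the arm for summaries presented by arm, and another reading leaves the control arm with no end date.

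**What to change.** Reconcile the two sentences in Section 6, and align the endpoint wording in the synopsis and Section 2.2:

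- Every by-arm safety summary uses one calendar window in both arms, from surgery on Day 0 through the Day 45 visit.
- Events between consent and surgery are listed separately.
- If the dose-anchored period is kept for SAE reporting, define the last study drug dose for each arm, and state that this period does not set the comparison window.

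The cost is a few sentences of text. No visit, assessment or data item is added, because both schedules already run to Day 45. The small downside is that control-arm events learned of after the Day 45 visit would be reported but not compared; no contact is scheduled in that period.
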